6.6.2. Multiplicity Control for EMA

Only for EMA purposes, two families for alpha control will be defined: 1 for induction and 1 for maintenance with each family-wise error rate at 0.05. So, different testing schemes will be used, 1 for the induction and another separate one for the maintenance period.

For all primary and major secondary endpoints for Induction Period, a prespecified graphical multiple testing approach (Bretz et al. 2009, 2011) will be implemented to control the overall Type I error rate at two-sided alpha of 0.05.

The following is a list of primary and major secondary endpoints to be tested for EMA for Induction Period.

Co-primary endpoints:

- [IGA01 W16] Percentage of patients with an IGA 0 or 1 and a ≥ 2 -point improvement from Baseline to Week 16.
- [EASI-75 W16] Percentage of patients achieving EASI-75 ($\geq 75\%$ reduction from Baseline in EASI score) at Week 16.

Major secondary endpoints for Induction Period:

- [EASI-90 W16] Percentage of patients achieving EASI-90 ($\geq 90\%$ reduction from Baseline in EASI score) at Week 16.
- [EASI PCFB W16] Percentage change in EASI score from Baseline to Week 16.
- [EASI-90 W4] Percentage of patients achieving EASI-90 at Week 4.
- [Pruritus PCFB W16] Percentage change in Pruritus NRS score from Baseline to Week 16.
- [Pruritus NRS-4 W16] Percentage of patients with a Pruritus NRS of ≥ 4 -points at Baseline who achieve a ≥ 4 -point reduction from Baseline to Week 16.
- [Pruritus NRS-4 W4] Percentage of patients with a Pruritus NRS of ≥ 4 -points at Baseline who achieve a ≥ 4 -point reduction from Baseline to Week 4.
- [Pruritus NRS-4 W2] Percentage of patients with a Pruritus NRS of ≥ 4 -points at Baseline who achieve a ≥ 4 -point reduction from Baseline to Week 2.
- [DLQI W16] Percentage of patients with a DLQI total score of ≥ 4 -points at Baseline who achieve a ≥ 4 -point improvement from baseline to Week 16.
- [DLQI CFB W16] Change from baseline in Dermatology Life Quality Index (DLQI) at Week 16.
- [Sleep loss W16] Percentage of patients with a Sleep-loss score ≥ 2 points at Baseline who achieve a ≥ 2 points reduction from Baseline at Week 16.
- [Sleep loss CFB W16] Change from Baseline in Sleep-loss score at Week 16.

Figure KGAB.6.3 describes the graphical testing scheme for Induction Period for EMA.

[figure not shown]

Figure KGAB.6.3. Graphical approach to control type 1 error rate for Study J2T-DM-KGAB for EMA purposes.

A separate set of major secondary endpoints will be considered at Week 52 (End of Maintenance). These secondary endpoints across the 2 different regimens will be tested following the hierarchical testing procedure with a pre-specified order, that is, inferential conclusions about secondary endpoints require statistical significance at the 0.05 significance level.

The hierarchy for the major secondary endpoints at Week 52 is as follows

Q2W Maintenance therapy:

- Percentage of patients from those re-randomized to Q2W maintenance therapy having achieved EASI-75 at Week 16 who continue to exhibit EASI-75 at Week 52 (EASI-75 calculated relative to baseline EASI score).
- Percentage of patients from those re-randomized to Q2W maintenance therapy having achieved IGA 0 or 1 and a ≥ 2 -point improvement from Baseline at Week 16 who continue to exhibit an IGA 0 or 1 and a ≥ 2 -point improvement from Baseline at Week 52.

- Percentage of patients from those with a Pruritus NRS of ≥ 4 -points at baseline and re-randomized to Q2W maintenance therapy having achieved ≥ 4 -point reduction from baseline at Week 16 who continue to exhibit ≥ 4 -point reduction from baseline at Week 52.

Q4W Maintenance therapy:

- Percentage of patients from those re-randomized to Q4W maintenance therapy having achieved EASI-75 at Week 16 who continue to exhibit EASI-75 at Week 52 (EASI-75 calculated relative to baseline EASI score).
- Percentage of patients from those re-randomized to Q4W maintenance therapy having achieved IGA 0 or 1 and a ≥ 2 -point improvement from Baseline at Week 16 who continue to exhibit an IGA 0 or 1 and a ≥ 2 -point improvement from Baseline at Week 52.
- Percentage of patients from those with a Pruritus NRS of ≥ 4 -points at baseline and re-randomized to Q4W maintenance therapy having achieved ≥ 4 -point reduction from baseline at Week 16 who continue to exhibit ≥ 4 -point reduction from baseline at Week 52.

Q2W Maintenance therapy:

- Percentage change in EASI score from baseline at Week 52 for those patients re-randomized to Q2W maintenance therapy at Week 16.

Q4W Maintenance therapy:

- Percentage change in EASI score from baseline at Week 52 for those patients re-randomized to Q4W maintenance therapy at Week 16.

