## 9.6. Multiplicity Considerations

The prespecified graphical multiple testing approach (Bretz, 2011) will be implemented to control the overall Type I error rate at 2-sided alpha of 0.05 for superiority tests for the hypotheses for the primary and major secondary endpoints. The graphical approach is a closed testing procedure; hence it strongly controls the family-wise error rate across all endpoints (Alosh, 2014). The major secondary endpoints will be pre-specified in the SAP prior to first unblinded efficacy analysis.

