### *EMA objectives:*

The Week 16 endpoints of IGA (0,1) and EASI-75 represent a primary endpoint family. The graphical testing scheme will sequentially test IGA (0,1) first, followed by EASI-75 before proceeding to test the major secondary endpoints during induction period. Details of the specific graphical testing scheme (including testing order, interrelationships, Type I error allocation for the major secondary endpoints, and the associated propagation) will be pre-specified in the SAPs prior to first unblinded efficacy analysis. A separate graphical approach may be employed for testing the maintenance period endpoints.

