Study Objective: To evaluate the safety and efficacy of lebrikizumab compared with placebo in patients with moderate-to-severe AD	
FDA Endpoints	EMA Endpoints

Other Secondary Endpoints Specific for Maintenance Period:
 
 Percentage of patients from those re-randomized having achieved EASI-75 at Week 16 who continue to exhibit EASI-75 at Week 52 (EASI-75 calculated relative to baseline EASI score) Percentage of patients from those re-randomized having achieved IGA 0 or 1 and a ≥ 2-point improvement from Baseline at Week 16 who continue to exhibit an IGA 0 or 1 and a ≥ 2-point improvement from Baseline at Week 52 Time to loss of EASI-50 in the subset of patients who were re-randomized at Week 16 (EASI-50 calculated relative to baseline EASI score) Time to loss of EASI-75 in the subset of patients who were re-randomized and achieved EASI-75 at Week 16 (EASI-75 calculated relative to baseline EASI score) Time to loss of IGA response, i.e., developing an IGA score ≥ 2 with 2 points deterioration of achieved IGA response at Week 16, in the subset of patients who were re-randomized and achieved IGA 0 or 1 and a ≥ 2-point improvement from Baseline at Week 16 	
Major Secondary Endpoints Specific for Maintenance Period:
 
 Percentage of patients from those re-randomized having achieved EASI-75 at Week 16 who continue to exhibit EASI-75 at Week 52 (EASI-75 calculated relative to baseline EASI score) Percentage of patients from those re-randomized having achieved IGA 0 or 1 and a ≥ 2-point improvement from Baseline at Week 16 who continue to exhibit an IGA 0 or 1 and a ≥ 2-point improvement from Baseline at Week 52 Percentage of patients from those with a Pruritus NRS of ≥ 4-points at baseline re-randomized having achieved ≥ 4-point reduction from baseline at Week 16 who continue to exhibit ≥ 4-point reduction from baseline at Week 52 Percentage change in EASI score from Baseline at Week 52 in the subset of patients who were re-randomized at Week 16 
Other Secondary Endpoints Specific for Maintenance Period:
 
 Percentage change in SCORAD (having achieved EASI-75 at Week 16) from baseline at Week 52 Percentage of patients from those with a Pruritus NRS of ≥ 5-points at baseline re-randomized having achieved ≥ 4-point reduction from baseline at Week 16 who continue to exhibit ≥ 4-point reduction from baseline at Week 52 Time to loss of EASI-50 in the subset of patients who were re-randomized at Week 16 (EASI-50 calculated relative to baseline EASI score) Time to loss of EASI-75 in the subset of patients who were re-randomized and achieved EASI-75 at Week 16 (EASI-75 calculated relative to baseline EASI score) Time to loss of IGA response, i.e., developing an IGA score ≥ 2 with 2 points deterioration of achieved IGA response at Week 16, in the subset of patients who were re-randomized and achieved IGA 0 or 1 and a ≥ 2-point improvement from Baseline at Week 16

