Abbreviations: ACQ-5 = Asthma Control Questionnaire 5-item version; AD = atopic dermatitis; BSA = body surface area; CDLQI = Children’s Dermatology Life Quality Index; DLQI = Dermatology Life Quality Index; EASI = Eczema Area and Severity Index; EQ-5D = standardized instrument developed by the EuroQol Group; EMA = European Medicines Agency; FDA = Food and Drug Administration; IGA = Investigator Global Assessment; POEM = Patient Oriented Eczema Measure; PROMIS = Patient-Reported Outcomes Measurement Information System; SCORAD = SCORing Atopic Dermatitis; SQAAQ= subcutaneous administration assessment questionnaire.

For Food and Drug Administration (FDA), primary and major secondary endpoints for Induction Period will be adjusted for multiplicity. For European Medicines Agency (EMA), primary and major secondary endpoints for Induction Period and major secondary endpoints for Maintenance Period will be adjusted for multiplicity separately (i.e. induction and maintenance endpoints will be tested separately). Details can be found in Section 6.6.

5. Study Design

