6.6. Multiple Comparisons/Multiplicity

6.6.1. Multiplicity Control for FDA

A prespecified graphical multiple testing approach (Bretz et al. 2009, 2011) will be implemented to control the overall Type I error rate at two-sided alpha of 0.05, for all primary and major secondary endpoints for FDA. Multiple testing adjusted p-values using “Algorithm 2” described by Bretz et al. (2009) will be calculated, and any hypothesis tests with a multiple testing adjusted p-value of less than 0.05 will be considered statistically significant. This graphical approach is a closed testing procedure; hence, it strongly controls the family-wise error rate across all endpoints (Bretz et al. 2009, 2011; Alosch et al. 2014). Each hypothesis is represented as a node in a graph. Directed arrows between the nodes with associated weights represent how alpha is passed from its initial allocation to other nodes.

The following is a list of primary and major secondary endpoints to be tested for FDA.

Primary endpoint:

- [IGA01 W16] Percentage of patients with an Investigator Global Assessment (IGA) score of 0 or 1 and a reduction ≥ 2 points from Baseline to Week 16.

Major secondary endpoints:

- [EASI-75 W16] Percentage of patients achieving EASI-75 ($\geq 75\%$ reduction from Baseline in Eczema Area and Severity Index [EASI] score) at Week 16.
- [EASI-90 W16] Percentage of patients achieving EASI-90 ($\geq 90\%$ reduction from Baseline in EASI score) at Week 16.
- [Pruritus NRS-4 W16] Percentage of patients with a Pruritus Numerical Rating Scale (NRS) of ≥ 4 -points at Baseline who achieve a ≥ 4 -point reduction from Baseline to Week 16.
- [Pruritus NRS-4 W4] Percentage of patients with a Pruritus NRS of ≥ 4 -points at Baseline who achieve a ≥ 4 -point reduction from Baseline to Week 4.
- [Pruritus NRS-4 W2] Percentage of patients with a Pruritus NRS of ≥ 4 -points at Baseline who achieve a ≥ 4 -point reduction from Baseline to Week 2.
- [IGA01 W4] Percentage of patients with an IGA score of 0 or 1 and a reduction ≥ 2 points at Week 4.

- [IGA01 Adult W16] Percentage of patients with an IGA score of 0 or 1 and a reduction ≥ 2 points at Week 16 in adults.
- [Sleep loss W16] Percentage of patients with a Sleep-loss score ≥ 2 points at Baseline who achieve a ≥ 2 points reduction from Baseline at Week 16.

Figure KGAB.6.2 describes the graphical testing scheme for FDA.

[figure not shown]

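### Does the promise of an overall 0.05 conflict with EMA testing in two families of 0.05 each?

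*SAP*

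**What the plan says.** The general statements:

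- Protocol 9.6 opens with the purpose of the graphical method: "control the overall Type I error rate at 2-sided alpha of 0.05 for superiority tests for the hypotheses for the primary and major secondary endpoints". It adds, as a property of a closed test, "hence it strongly controls the family-wise error rate across all endpoints". It leaves the list of major secondary endpoints to the SAP.
- SAP 6.11.1, the section on the primary outcome, also speaks of an overall two-sided 0.05 for primary and major secondary objectives, by a graphical approach, and sends the reader to Section 6.6.

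The specific statements for EMA:

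- Protocol 9.6, EMA objectives: "The graphical testing scheme will sequentially test IGA (0,1) first, followed by EASI-75 before proceeding to test the major secondary endpoints during induction period". Then: "A separate graphical approach may be employed for testing the maintenance period endpoints". No alpha is named for that separate approach, and the allocation of alpha to the major secondary endpoints is left to the SAP.
- SAP Section 4: for EMA, "primary and major secondary endpoints for Induction Period and major secondary endpoints for Maintenance Period will be adjusted for multiplicity separately". Table KGAB.4.1 lists the Week 52 endpoints under "Major Secondary Endpoints Specific for Maintenance Period".
- SAP 6.6.2: "two families for alpha control will be defined: 1 for induction and 1 for maintenance with each family-wise error rate at 0.05". The induction family is tested by a graph. The Week 52 family is tested in a fixed order at 0.05.

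For FDA, SAP 6.6.1 sets up its graph "to control the overall Type I error rate at two-sided alpha of 0.05, for all primary and major secondary endpoints for FDA", and its list contains induction endpoints only.

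**The concern.** Protocol 9.6 lets the SAP define the major secondary endpoints, and the SAP puts EMA's Week 52 endpoints among them. The general promise of one overall 0.05 therefore appears to cover them. Section 6.6.2 gives them a second 0.05, with no split of alpha and no gate from the induction family. Two families at 0.05 do not add up to an overall 0.05.

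SAP 6.11.1 looks the more exposed of the two general statements. It names EMA's additional EASI-75 hypothesis, so it is not an FDA-only sentence, and unlike 6.6.1 and 6.6.2 it does not limit its claim to one regulator or one period. At stake is how the EMA Week 52 results are described: a report author who quoted the general sentence alone would present them as covered by a study-wide 0.05, when they are controlled only within the maintenance family.

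**Working it through.** **Inputs.** Alpha for EMA induction 0.05 and for EMA maintenance 0.05 (SAP 6.6.2). Order of the EMA co-primary tests (Protocol 9.6, EMA objectives). Planning rates and group sizes (SAP 5.2).

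**Step 1: the plan's own figure.** Within one family the error rate is 0.05, as stated. The fixed order for Week 52 gives this directly, because the first true null hypothesis reached is tested at 0.05 and a failure stops the sequence. For induction the 0.05 is taken as stated, because Figure KGAB.6.3 is not shown.

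**Step 2: both families together.** Let a be the alpha held by a true null hypothesis in induction, and let the first Week 52 test also be null.

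- If the families are independent: 1 − (1 − a)(1 − 0.05). With a = 0.05 this is 1 − 0.95 × 0.95 = 0.0975.
- Under any dependence: at most a + 0.05 = 0.05 + 0.05 = 0.10.
- If every induction effect is real, a = 0 and the result is 0.05.

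A simulation of 2,000,000 draws of the first test in each family, taken as independent, gave 0.0976. Independence is an approximation. It is reasonable here because the Week 52 arms come from a new randomization at Week 16.

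**Step 3: when the maximum arises.** IGA is tested first, then EASI-75, before any secondary. A null IGA, or a null EASI-75 after a real IGA effect, would hold the full 0.05. The first Week 52 test must be null as well. The planning figures do not point that way. With 96 and 48 patients and a continuity-corrected chi-square test, power is 95.2% for IGA (34.7% against 7.7%) and 99.6% for EASI-75 (48.0% against 11.5%). Both match the stated value of more than 95%, and about 400 patients are planned. For a null among the induction secondaries, a depends on graph weights that cannot be read here, so the result lies somewhere from 0.05 to 0.0975 under independence.

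**Step 4: do the passages conflict in use?**

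| Question for the analyst | Where it is answered |
|---|---|
| Are the EMA periods tested jointly or separately? | SAP Section 4 and 6.6.2: separately |
| At what level? | SAP 6.6.2: 0.05 in each |
| By what procedure? | SAP 6.6.2: graph for induction, fixed order for Week 52 |
| Does the Protocol permit a separate maintenance scheme? | Protocol 9.6, EMA objectives: yes |
| Does SAP 6.11.1 set its own rule? | No, it refers to Section 6.6 |

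No two entries would lead an analyst to different tests or different thresholds.

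**Step 5: what a literal overall 0.05 would need.** The two alphas would have to sum to 0.05. For example, 0.025 + 0.025 gives a bound of 0.05, and 1 − 0.975² = 0.0494 under independence. That is another design. The SAP does not plan it, and the concern does not ask for it.

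**The case for a change.** The strongest case for a change is that disclosure in one section does not make a contrary sentence elsewhere true. The Protocol's allowance for maintenance is only a possibility and names no alpha, and a separate graph could have run inside a shared 0.05. The cross-reference in SAP 6.11.1 can be read as saying how the overall 0.05 will be achieved, not as narrowing it. The SAP limits the same claim correctly in 6.6.1 (FDA) and in 6.6.2 (induction), so leaving the limit out of 6.11.1 is a slip. Correcting it would cost one clause.

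Part of this stands. The sentence in 6.11.1 is loose on the error rate. It is also loose on method, since it speaks of a graph while the Week 52 endpoints follow a fixed order. That second mismatch counts against the literal reading, however. The graphs in Section 6.6 are those for FDA and for EMA induction, and for each of them 0.05 is the correct figure. The section states null hypotheses for Week 16 only.

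The Protocol 9.6 sentence is an introduction to two regulator-specific schemes, and its statement about all endpoints describes a property of a graphical closed test, so it applies to the endpoints within a graph. The EMA text under the same heading limits the scheme to induction. It is therefore not accurate to say that the Protocol makes its claim without limit. The risk of misquotation in the report is real but small, because any description of the EMA Week 52 testing has to draw on 6.6.2, where the procedure and its level are set out.

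**Conclusion.** No change to the plan is called for. The arithmetic behind the concern is right: across both EMA families the error rate can reach 0.0975 under independence and is bounded by 0.10, against 0.05 on a literal reading of the general sentences. Separate control by period is a legitimate choice that the SAP states openly in two places, and each family keeps its own 0.05. The gap lies between loose general sentences and an explicit specific rule, and the specific rule governs. Following 6.6.2 exactly gives the same tests, order, thresholds and conclusions whether or not the general sentences are tightened. SAP 6.1 requires a protocol amendment only when a principal feature changes, and none does here. When the clinical study report describes EMA Week 52 findings, the accurate phrase is control within the maintenance family. That already follows from 6.6.2.

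This rests on two assumptions: that 6.6.2 is applied as written, and that the induction graph, whose figure is not shown, keeps its family at 0.05 as stated.

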6.7. Patient Disposition

The following patient disposition summaries will be provided (details of the analysis populations can be found in Section 6.1.1):

- Total number and percentage of patients entering each statistical analyses population defined in Section 6.1.1.
- The number and percentage of patients who entered the study, failed screening, were randomized at Baseline Visit (Day 1), completed Week 16, completed Week 52, completed the safety Follow-Up Visit and entered long-term extension study. Summary will be provided by the initial randomized treatment group (Analysis population: Intent-to-Treat [ITT]).
- The number and percentage of patients who completed the study, and the number and percentage of patients who discontinued the study at any time, by the initial randomized treatment group and primary reason for discontinuation (Analysis population: ITT).
- The number and percentage of patients who completed Induction Period and the number and percentage of patients who discontinued from Induction Period, by treatment group and primary reason for discontinuation (Analysis population: ITT).

- The number and percentage of patients who completed Maintenance Period and the number and percentage of patients who discontinued from Maintenance Period, by treatment group and primary reason for discontinuation (Analysis populations: Maintenance Primary Population and Maintenance Secondary Population), in addition, the number and percentage of patients who entered the escape arm will be summarized for Maintenance Primary and Secondary Population.

All patients who were randomized (that is, in the ITT population) and discontinued from study treatment during any period from the study will be listed together with the discontinuation reason, and the timing of discontinuation from the study will be reported.

Patient allocation by region, country, and center/site will be summarized with number of patients who entered the study, number of ITT patients for each treatment group, number of patients discontinued from study treatment, and number of patients discontinued from the study.

6.8. Patient Characteristics

6.8.1. Demographics and Baseline Characteristics

Patient demographic variables and baseline characteristics will be summarized by treatment group for the ITT population, the Maintenance Primary Population, and the Maintenance W16 Escape Population. The continuous variables will be summarized using descriptive statistics and the categorical variables will be summarized using frequency counts and percentages. No formal statistical comparisons will be made between treatment groups unless otherwise specified.

The following demographic information will be included:

- Age
- Age group (Adolescents (12<18), Adults ≥ 18)
- Age group (Adolescents (12<18), Adults $\geq 18 - < 65$, $\geq 65 - < 75$, ≥ 75)
- Sex (male, female)
- Race (American Indian or Alaska Native, Asian, Black or African American, Native Hawaiian or Other Pacific Islander, White, Multiple, Other, Not Reported)
- Ethnicity for US (Hispanic or Latino, Not Hispanic or Latino, Not reported, Unknown)
- Region (as defined in Section 6.3)
- Country
- Weight (kg)
- Weight category (<60 kg, ≥ 60 to <100 kg, ≥ 100 kg)
- Height (cm)
- Body mass index (BMI) (kg/m^2)
- BMI category: Underweight (<18.5 kg/m^2), Normal (≥ 18.5 and <25 kg/m^2), Overweight (≥ 25 and <30 kg/m^2), Obese (≥ 30 and <40 kg/m^2), Extreme obese (≥ 40 kg/m^2)

By-patient listings of basic demographic information for the ITT population will be provided.

The following baseline disease/clinical characteristics will be included:

- Age at onset (years): calculated as the difference between date of onset of AD and the date of birth collected on the CRF.
- Duration since AD onset (years): calculated as the difference between date of Informed Consent and the date of onset of AD collected on the CRF.
- Duration since AD onset category (0 to <2 years, 2 to <5 years, 5 to <10 years, 10 to <20 years, ≥ 20 years)
- Anatomical area affected by atopic dermatitis:
 - Head
 - Trunk (internal/medial axillae and groin)
 - Upper extremities (includes external axillae)
 - Lower extremities (includes buttocks and feet)
 - At least 2 areas
- Atopic Dermatitis treatment used in the past
 - None
 - Topical corticosteroids
 - Topical calcineurin inhibitors
 - Immunosuppressive/immunomodulating drugs: systemic corticosteroids; cyclosporine; mycophenolate-mofetil; IFN- γ ; janus kinase inhibitors; azathioprine; methotrexate
 - Phototherapy
 - Photochemotherapy (PUVA);
 - Other Biologics (e.g., cell depleting biologics)
 - Other non-Biologic medication/treatment
- Prior use of systemic treatment (yes, no) Investigator's Global Assessment for AD (IGA) score: 3 versus 4
- Eczema Area and Severity Index (EASI) score
- SCORing Atopic Dermatitis (SCORAD)
- Body Surface Area (BSA)
- Pruritus NRS
- Pruritus NRS: <4, ≥ 4

- Pruritus NRS: $<5, \geq 5$
- Sleep loss due to pruritus
- Sleep loss due to pruritus: $<2, \geq 2$
- Patient-Oriented Eczema Measure (POEM)
- Dermatology Life Quality Index (DLQI)
- Children Dermatology Life Quality Index (CDLQI)
- EQ-5D Visual Analog Score (VAS) score
- EQ-5D US Population-based index score
- EQ-5D UK Population-based index score
- Patient-Reported Outcomes Measurement Information System (PROMIS®) Anxiety and Depression scores
- Asthma Control Questionnaire (ACQ-5) (among patients who report comorbid asthma)

